## **6.2 Study duration and time planning**

It will start as soon as possible after the positive decision of the ethics committee. Expected on 07.01.2019. Respectively as soon as possible after the positive decision of the ethics committee. The last patient will complete the intervention on 26.04.2019. Thereafter, the data is evaluated.

The positive decision of the ethics committee arrived at 19.12.2018.

## **6.3 Methods to minimize bias**

All physiotherapists were trained twice in the scheduled assessments. The colleague, who is to represent me in the balance training, was enrolled and the program already included by default in the balance group. If necessary, it will be retrained.

All colleagues, including nurses and doctors have received detailed information on the planned pilot study in the course of an information event and will be informed shortly before the start, if there are changes due to the ethics application.

The randomization was prepared and the sealed envelopes numbered in order.

## **6.4 Randomization**

The randomization was prepared and the sealed envelopes numbered in order. Randomization was done using a list randomizer (<https://www.random.org/lists/>). The list is not publicly available.

## **6.5 Mask, Blinding**

There is no blinding. Compliance with the blinding is hardly feasible in this setting. The patients recognize which group they are in and the group room is freely accessible and accessible by my colleagues.

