## **6 DESIGN AND EXPIRATION OF THE STUDY**

### **6.1 General design and justification of the design**

A controlled, randomized, open pilot study with parallel group design will be conducted.

In each case, ten patients are recruited randomly into the intervention group or control group. It does not pay attention to gender distribution. Each patient takes about three to four weeks to participate in the study. There are three weeks of intervention time.

The screening begins with the registration of the patient, because then usually already a preliminary discharge report, or referral report exists. On the day of arrival the medical admission takes place and the screening is checked. On the second day the Investigator visit the patient and explain to him about the possible participation in the study. He receives the consent form with the explanations from me and is informed that he will answer further questions, e.g. for medical safety to the attending physician could turn. With the signed consent, the randomization and accordingly the planning of the therapies, including initial and reassessment. Depending on the day of arrival, the intervention may begin in the first or second week. With the allocation, the therapists will also be informed, since they are not allowed to do any additional balance training in the therapy. When the sixth balance training is done, the reassessment takes place the next day.

This is an ongoing process for each patient.

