### Walking speed

The walking speed is measured using the 10m walk test. This has a high reliability for stroke patients (Flansbjerg, Holback, Downham, Patten, & Lexell, 2005).

The patient walks a distance of 20m. The start and end points are each marked with a cone. The patient is asked to walk this route as fast as possible, but so that he feels safe. The measurement begins as soon as one of the lower extremities crosses the 5m mark and stops when one of the lower extremities crosses the 15m mark. The therapist goes with the patient to see this. This is to exclude the startup and stopping delays (Schädler, et al., 2012). Three consecutive passes are taken to calculate the mean.

This gives you the walking speed in m / sec if you calculate 10m divided by the seconds. If an aid was needed to go, this will be noted.

This test has high reliability with an ICC of 0.94-0.97 (Flansbjerg, Holback, Downham, Patten, & Lexell, 2005).

In addition, stroke abilities were classified as having everyday abilities (Perry, Garrett, Gronley, & Mulroy, 1995).

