### 8.2.1 Recording of the primary target

The walking speed is tested one day before the first IB or GB and one day after the last IB / GB. So a training effect that could falsify the result should be avoided. It is measured by a physiotherapist.

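### No safeguard keeps the trainer or an informed treating therapist from measuring the outcomes; the reasons given make assessor masking difficult, not impossible

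*Combined protocol and SAP*

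**What the plan says.** - **Blinding.** Section 6.5 states "There is no blinding. Compliance with the blinding is hardly feasible in this setting". It gives two reasons: "The patients recognize which group they are in", and "the group room is freely accessible and accessible by my colleagues". It does not discuss masking of assessors separately from masking of patients.
- **Who measures.** Section 8.2.1 says of walking speed only "It is measured by a physiotherapist". Section 8.2.2 says the same for the risk of falling. Neither sets a condition on the tester's role or knowledge of the arm.
- **Who knows the arm.** Under section 3.2 the investigator delivers the balance training, with a trained employee as stand-in. Under section 7.3 the investigator is shown the assignment when the envelope is opened. Section 6.1 adds "With the allocation, the therapists will also be informed".
- **Who could measure.** Section 6.3 says "All physiotherapists were trained twice in the scheduled assessments". Section 8.2 adds that they all have at least half a year of experience with the tests.
- **The test.** Under Walking speed in section 8.2: "The patient is asked to walk this route as fast as possible, but so that he feels safe". On the 5 m and 15 m crossings: "The therapist goes with the patient to see this". Three passes are averaged.
- **Use of the data.** Section 10 feeds the pilot data into G*Power to size a later trial.

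**The concern.** The walk test is a fast-pace test, so the result depends partly on how the patient is urged on and how the two crossings are judged. The protocol prescribes no wording for encouragement. The 14 BBS items are each scored 0 to 4 by the assessor, and the Functional Ambulation Categories (FAC) are a rating. The synopsis states a hypothesis in favour of individual training. As written, the person who holds that hypothesis, delivers the training and knows the assignment may also time the walk and score the balance scale.

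If knowledge of the arm shifts the measurements, the shift has a direction, and recruiting more patients does not remove it. It would enter the effect size carried into the follow-up calculation. The protocol aims to uncover bias (sections 4.1 and 10.3), yet it does not plan to record whether the tester knew the arm. This particular bias could therefore not be examined afterwards.

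**Working it through.** The plan has no figure to reproduce here. Section 10.2 sets 20 patients from the time available and gives no alpha, power or SD. The check is mainly a comparison of sections, followed by an illustration.

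**1. Do the reasons in 6.5 rule out masked assessment?**
- Patients knowing their group rules out masking patients. It does not stop a tester from being left untold, although a patient may reveal the arm.
- The open group room means a colleague may see who attends. This concerns possible assessors, so it is a real obstacle. It shows that unmasking can happen, not that it must.
- Neither reason concerns whether the trainer should be the tester. The trainer always knows the arm.

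**2. Does any section exclude those who know the arm from testing?** Sections 6.3, 6.5, 8.1, 8.2.1 and 8.2.2 do not. Section 8.1 mentions the BBS and the walk test within physiotherapy once the patient has signed. This suggests, without stating it, that the treating therapist may do the tests.

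**3. Must therapists be told the arm?** Section 6.1 gives the ban on extra balance training as the reason for informing them. The synopsis words that ban identically for both arms, and section 7.9 drops the seat-and-stand group for both. A therapist needs to know that the patient is in the study, not in which arm.

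**4. Is baseline exposed?** Section 8.1 opens the envelope on the day of consent and tests the day after. The time plan in the synopsis lists the tests before the envelope. The two must be reconciled. Under the section 8.1 order, baseline can also be measured by someone who knows the arm.

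**5. Illustration of size.** Every input is assumed except that 0.18 m/s is borrowed from section 5.1, where it is an improvement in walking speed and not a difference between arms.
- True between-arm difference δ = 0.18 m/s; SD of 0.2, 0.3 or 0.4 m/s; two-sided 5%, 80% power, 1:1.
- Assessor shift towards individual training b = 0.02, 0.05 or 0.09 m/s.
- Normal approximation: n per arm = 2(1.96 + 0.84)² SD²/δ². A pilot that shows δ + b leads to a planned n that is a fraction (δ/(δ + b))² of the n required, whatever the SD.
- b = 0.02: (0.18/0.20)² = 0.81. b = 0.05: (0.18/0.23)² = 0.61. b = 0.09: (0.18/0.27)² = 0.44.

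| SD (m/s) | n per arm required | n planned, b = 0.02 | n planned, b = 0.05 | n planned, b = 0.09 |
|---|---|---|---|---|
| 0.2 | 20 | 16 | 12 | 9 |
| 0.3 | 44 | 36 | 27 | 20 |
| 0.4 | 78 | 63 | 48 | 35 |
| True power | 0.80 | 0.71–0.72 | 0.60 | 0.47–0.48 |

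The t-based calculation adds one patient per arm to every n in the table and leaves the power figures essentially unchanged.

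The result depends strongly on the assumed true difference. With a true difference of 0.05 m/s, SD 0.2 and a shift of 0.05 m/s, d goes from 0.05/0.2 = 0.25 to 0.10/0.2 = 0.50, and the t-based n falls from 253 to 64 per arm. That case sets the bias equal to the true effect, so it should not be taken as typical.

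**The case against.** The strongest reply is that section 6.5 does address assessors: colleagues can walk into the group room, and colleagues are the only possible testers. Section 6.3 adds that all colleagues were briefed on the study, and section 6.1 that therapists are informed with the allocation. No staff numbers are given, so it is not shown that an unaware physiotherapist would always be free. This stands. It limits the remedy to incomplete masking, with a non-treating tester where possible.

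Second, the trial is openly labelled an open pilot, section 10.1 concedes that only a guess is possible, and the tests were trained and reviewed, with fixed marks and three passes. This lowers the severity. Standardisation limits random error and some discretion, but it does not remove the effect of knowing the arm.

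Third, sampling error is large anyway. With 10 per arm and an assumed SD of 0.2 m/s, the standard error of the difference is 0.2 × √(2/10) = 0.09 m/s. Patients also know their arm in a test that depends on effort, and a masked tester does not change that. Both points are right. They mean the fix removes one source of error among several.

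A reader might infer more than the documents support in two ways. One is that the reasons in 6.5 concern only patients and trainers, so that masked assessors are readily at hand. The sentence about colleagues contradicts this, and trainers are not mentioned in 6.5. The other is that the follow-up trial will be too small. That would need an actual shift towards individual training, and the documents show neither its existence nor that the physiotherapists share the investigator's hypothesis.

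**Conclusion.** The concern holds in a limited form. The plan allows the trainer, the deputy or a treating therapist who knows the arm to measure an effort-dependent primary outcome and an assessor-scored secondary one, and it plans no safeguard. The reasons in 6.5 explain why masking in-house assessors is difficult; they do not show it to be impossible, and they do not support using testers who are certain to know the arm.

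The size of any bias cannot be derived from the documents. On the assumptions shown, shifts of 0.02 to 0.09 m/s would leave about 81% to 44% of the required n; other assumed values give other results. This is a worthwhile, inexpensive improvement to a pilot whose data will size a later trial. It does not invalidate the design.

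**What to change.** In sections 6.5, 8.2.1 and 8.2.2:
- State that the investigator and the deputy who deliver the training do not perform the 10 m walk, BBS or FAC, at baseline or at reassessment.
- State that another physiotherapist already trained in the tests performs them, where possible not the one treating that patient, and that this person is not told the arm.
- In section 6.1, limit the information given to therapists to study participation, which is enough for the ban on extra balance training.
- Ask patients not to reveal their group to the tester.
- Record on the CRF who tested and whether that person knew the arm, and list this among the biases to be examined under section 10.3.
- Reconcile the order of baseline tests and envelope between the synopsis and section 8.1.

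The cost is a rota rule and a short CRF entry. Because all physiotherapists are already trained in the tests and only two people deliver the training, the basic rule calls for no additional assessor. The drawbacks are some scheduling effort and incomplete masking in a small clinic. Patients remain unblinded.

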# **7 PARTICIPANTS**

Adult patients with strokes from rehabilitation phase B are recruited as long as they are able to walk with aids. It is a monocentric study in the RehaClinic Kilchberg. There, a total of 20 patients will be recruited over a 3-month period. Since it is a pilot study, I would look for a solution in the discussion, if the number of participants would not be reached. The patients who are already inpatients are recruited insofar as the discharge date is far enough in the future and the patients who have recently arrived there.

## **7.1 Eligibility criteria**

### **7.1.1 Inclusion criteria**

Patients who meet all of the following inclusion criteria may be included in the clinical trial.

- min. 18 years
- stroke starting from Rehaphase B
- ability to understand therapy instructions
- walkable with aids

### **7.1.2 Ausschlusskriterien**

If one or more of the following exclusion criteria is met, the individual can not be included in the clinical trial.

- Neurodegenerative disease
- non-stroke dizziness
- cardiopulmonary insufficiency
- polyneuropathy
- peripheral vascular disease
- Known or suspected non-compliance with the protocol, drug or alcohol use
- Inability of the patient to follow the experimental procedure, e.g. because of language problems, mental illness, dementia etc.

## **7.2 Recruiting and screening**

The screening begins with the registration of the patient, because then usually already a preliminary discharge report, or referral report exists. On the day of arrival the medical admission takes place and the screening is checked. On the second day I visit the patient and explain to him about the possible participation in the study. He receives the informed consent with explanations from me.

There is no compensation for participation in this pilot study.

## **7.3 Assignment to study groups**

The randomization was prepared and the sealed, opaque envelopes numbered in order. The randomization list is not public. Only I have access to it. The procedure is based on the order of consent, so that the allocation can not be manipulated.

After signing the consent form, I go with this to one of my direct supervisor ([name]) show her the consent and give them access to the envelopes (in a lockable closet). You open the envelope and show me which group has been assigned. I label the envelope and lock it again and lock it into my spint.

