Study period:	It will start as soon as possible after the positive decision of the ethics committee. Expected on 07.01.2019. The last patient will complete the intervention on 26.04.2019. The positive decision of the ethics committee arrived at 19.12.2018.

Timeplan:	
 
▪ I check the submitted reports one day before arrival, if the patient is suitable and inform the doctors (head doctor, senior physician and assistant doctors of the ward)
 
▪ The doctors check this again on the admission day and give me feedback
 
▪ I go to the patient on the second day and inform him / her about the ongoing study and give him / her the consent
 
▪ If the patient has signed, the berg balance scale and the 10m walk test will be performed on the same or the next day and the envelope will be drawn for randomization.
 
▪ Then he will be assigned at the next opportunity so that he gets the balance training twice a week
 

Investigator:	
[name], Physiotherapist, BA  [name], [name], Switzerland  [contact]  [name]

Study location:	
RehaClinic Kilchberg, [name], [name], Switzerland

Statistic Analyses:	
It is applied by the low descriptive statistics record and the SampleSize is determined. It uses SPSS version 25 and G * Power Vers. 3.1.9.2

GCP:	
This clinical trial will be conducted in compliance with the protocol, the current version of the Helsinki Declaration and ICH-GCP, as well as national guidelines and legislation.

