## **2.5 Participant information and consent**

The investigator must explain to each participant the nature and purpose of the clinical trial, the intended actions, the likely duration, the benefits and possible risks, and any inconvenience this may cause. Each participant must be informed that participation in a clinical trial is voluntary, that he / she may terminate the activity at any time, and that withdrawal of the consent will not interfere with his / her subsequent medical treatment / care.

The study participant must be informed that his / her medical records can be inspected by other, authorized persons in addition to the attending physician.

All study participants will be provided with participant information and a declaration of consent, which describes the study and contains sufficient information so that the participants can make an informed decision about their study participation.

The participant information and informed consent will be presented together with the study protocol for review and approval by the Competent Ethics Committee and Swissmedic. The formal consent of a participant must be obtained before the participant participates in any study activity. The approved consent form must be used for this purpose.

The participant should read and rethink the information before signing and dating the consent form. The consent form must also be signed and dated by the investigator or his deputy and kept as part of the study documentation.

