### **12.1.1 case report forms**

For each test participant, the examiner performs a paper case report form (CRF) in which all test-relevant data of a participant are entered. All participants (subjects enrolled in the study, non-clinical subjects, or non-admitted individuals eligible for the clinical trial) will be documented in a screening log. The investigator notes a person's participation in a special enrollment log.

CRFs need to be kept up-to-date to reflect the status of a participant at each stage of the study. The name of the test participant may not be visible in the CRF. Use appropriate coding (e.g., subscriber number).

It must also be ensured that anyone who can make entries and corrections in the CRF can be identified. A list with the signature and abbreviation of all authorized persons is stored in the Investigator Site File and the central reviewer.

The documented medical history and written statements on the status of the participant during the clinical trial should be kept together with the CRF of the participant concerned. These records may also include: originals or copies of laboratory results, other medical tests (e.g., ECG), etc.

The test persons ensure complete and correct documentation of the participant data in the CRF. All data entered into the CRF must also be included in the patient record, either as printouts or as notes by the investigator or by another person delegated by the investigator.

All essential clinical trial documents must be kept for a minimum of 10 years after the end or termination of the clinical trial.

The medical records and other original data must be kept for the longest possible period of time allowed by the hospital, institution or private practice.

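### The investigator who recruits is also the only holder of the randomisation list, and the schedule draws the envelope before the baseline walk test

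*Combined protocol and SAP*

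**What the plan says.** **List and envelopes.** Section 7.3 describes sealed, opaque, numbered envelopes in a lockable closet. After consent the investigator shows the signed form to a supervisor and gives that supervisor access; the supervisor opens the envelope. On the list: "The randomization list is not public. Only I have access to it". On the safeguard: "The procedure is based on the order of consent, so that the allocation can not be manipulated". On the opened envelope: "I label the envelope and lock it again and lock it into my spint". Section 6.4 names an online list randomiser but no independent person who generates or holds the list.

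**Who recruits.** The synopsis timeplan says "I check the submitted reports one day before arrival, if the patient is suitable and inform the doctors". Section 7.2 says "On the second day I visit the patient and explain to him about the possible participation in the study", and 6.1 assigns that same visit to the investigator, so the first person in 7.3 is the investigator. Recruitment is not confined to new arrivals; section 7 says "The patients who are already inpatients are recruited insofar as the discharge date is far enough in the future".

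**Draw and baseline.** The table in 8.1 puts the draw, the report to scheduling and the notification of the patient on the day of signed consent (SC). The 10 m walk test, Berg Balance Scale (BBS) and FAC follow on SC +1d, and training on SC +2d. Section 6.1 also ties randomisation to signed consent. The synopsis names the tests first and the envelope after them. Section 6.5 states that the trial is open.

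**The concern.** Concealment means that the person deciding whether and when to enrol a patient cannot know the next arm. Here that person can look it up, and also expects individual training to do better (synopsis hypothesis, section 3), delivers the training (3.2) and analyses the data (10.3.2). The assurance in 7.3 therefore does not cover enrolment by the investigator.

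The second issue is the baseline. The walk test asks for the fastest pace at which the patient still feels safe, so it depends on effort and encouragement. In an open trial the reassessment is unavoidably taken with the arm known, but the baseline need not be. If it is, any difference in effort between arms passes one for one into the change in walking speed.

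At stake are the pilot's purpose of detecting bias (4.1, 10.3), its first comparison of the arms and, on one condition, the sample size of the follow-up trial (section 10).

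**Working it through.** The plan gives no figure on this point to reproduce. The core of the check is a reading of the text; the arithmetic only gives scale.

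**1. What each safeguard covers**
- Opaque envelopes hide the arm from anyone without the list. The investigator has the list.
- Consent order and opening by a supervisor prevent a swap once a patient has signed.
- None of these governs who is approached, or when. For new arrivals the day-2 visit and the doctors' recheck of eligibility limit the room. For patients already in the clinic no day is fixed.

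**2. Order of draw and baseline**
- 8.1: draw and notification on SC, tests on SC +1d.
- 8.1, 2nd-day row: tests allowed once consent is signed; order relative to the draw left open.
- 6.1: randomisation at signed consent, followed by planning that includes the initial assessment.
- Synopsis: tests, then envelope, but joined only by *and*.

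Two places put the draw first. The synopsis differs only by the order in which it lists the steps.

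**3. Predictability** (assumption: one fixed 10:10 list and no replacements; 6.4 does not say this and 7.4 allows replacements)
- With the list: 20 of 20 allocations can be known in advance.
- Without it, the best guess from past assignments is 10 + 2^19/C(20,10) − 0.5 = 12.3 of 20.

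**4. Effect of one steered pair** (d and p are assumptions). One patient goes to each arm, their gains differ by d, and the better responder is correctly picked with probability p. The expected shift in the arm difference is (2p − 1)d/10.

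| d (m/s) | p = 0.7 | p = 1 (upper bound) |
|---|---|---|
| 0.10 | 0.004 | 0.010 |
| 0.20 | 0.008 | 0.020 |
| 0.36 | 0.014 | 0.036 |

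Chance, with 10 per arm: SE = SD × √(2/10). For an assumed SD of 0.15, 0.20 or 0.25 m/s this is 0.067, 0.089 or 0.112 m/s. At SD 0.20 the shifts are 4% to 16% of one SE for p = 0.7, and 11% to 40% for p = 1.

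**5. Follow-up sample size.** Section 10 names G*Power but not the input. If a fixed target difference is entered, a shift in the mean leaves n unchanged. If the observed difference is entered (assumed true difference 0.10, SD 0.20, two-sided 5%, 80% power), the base is 64 per arm. The p = 0.7 shifts give 60, 55, 49 in one direction and 70, 76, 87 in the other. One SE of chance alone gives 19 or about 5,600.

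**6. Baseline shift.** The documents give no basis for sizing it.

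**7. Scheduling window.** Sections 7.6.1, 7.6.2, 8.2.1 and 8.2.2 place the baseline one day before the first session. At present: draw on SC, training on SC +2d, two days. With the test first on SC +1d: draw SC +1d, training SC +2d, one day. With the test first on SC: draw SC, training SC +1d, one day.

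**The case against.** The strongest reply on concealment is that the sentence in 7.3 is about the order of consent and, for a patient who has already signed, is defensible. That stands; what it does not cover is the earlier step of choosing whom to approach and when. Steering is also constrained: doctors recheck eligibility, and on consent "The participant should read and rethink the information before signing and dating the consent form". It is partly auditable too: everyone considered "will be documented in a screening log", and consents are dated. Those records could be compared with the upcoming arm, but could not show why someone was approached late or not at all.

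A reader might infer that allocation was manipulated, or that the list was consulted. The documents do not support this. They show access only.

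On the baseline, a reader might infer a flat contradiction between the synopsis and 8.1. That is too strong, because the synopsis orders the steps only by listing them. Baseline tests are done by trained physiotherapists to a standard procedure with three passes averaged, which may limit a shift but does not remove knowledge of the arm. There may also be a practical reason for drawing first: the baseline must fall the day before the first session, and the group meets only twice a week, so the date is easier to set once the arm is known. That is an inference, since group days are not stated, but the fix has to allow for it.

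**Conclusion.** Both parts hold in limited form. First, the one person who pre-screens, approaches and consents can look up the next arm, so the assurance in 7.3 does not extend to enrolment by that person. Second, followed as written, 8.1 has an effort-dependent baseline taken with the arm known, although baseline is the measurement that an open trial can still protect.

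The likely numerical effect is small: one steered pair is well under one standard error in every assumed case, and d, p, SD and the true difference are all assumptions. A reader might infer that the follow-up sample size will be wrong. That follows only if the observed difference is entered, which the plan does not state, and chance would then dominate. The damage is mainly to a pilot whose declared purpose is to find sources of bias, and whose procedures may be carried into a larger trial. It should be fixed; it does not invalidate the pilot.

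**What to change.** **Concealment (6.4, 7.3).** Replace the existing list. An existing staff member with no role in recruiting, treating or analysing participants generates a new one, prepares the envelopes and holds the closet key. The investigator has no access to list or closet until recruitment ends. Replace the sentence on manipulation with a statement of who holds what.

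**Replacements (7.4).** A replacement now takes the vacated place, whose arm is already known in an open trial. Have the replacement take the next unused sealed envelope, and prepare spares.

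**Order.** Reconcile the synopsis timeplan, 6.1, 8.1, 8.2.1 and 8.2.2 to one sequence: signed consent; walk test, BBS and FAC recorded in the CRF; envelope opened; then patient, therapists and scheduling informed.

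**Cost.** A signed amendment with ethics approval (2.8, 12.1), since approval had already arrived on 19.12.2018. A small task for one staff member, whose availability and independence must be confirmed; section 11 mentions a research department but not whether it can do this. The time from draw to first session falls from two days to one, whichever day the test is done. The baseline must therefore be timed to suit both an individual slot and a group session, or 8.2.1 and 8.2.2 must allow a short stated interval. Without one or the other, some baselines might have to wait or be repeated.
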